## 7.13 Adverse Events

### 7.13.1 Definitions of Adverse Events (AEs)

An AE is any untoward medical occurrence that occurs in a patient or clinical investigation patient administered a pharmaceutical product, and which does not necessarily have to have a causal relationship with this treatment. An AE can therefore be any unfavourable and unintended sign (including abnormal laboratory finding), symptom, or disease temporally associated with the use of an investigational product, whether or not considered related to the product.

All AEs, including undercurrent illnesses, occurring during the study will be documented in the eCRF system. Concomitant illnesses, which existed before entry into the study, will not be considered AEs unless they worsen during the treatment period. All AEs, regardless of the source of identification (e.g., physical examination, laboratory assessment, ECG, reported by patient), must be documented. Worsening of the underlying disease is not considered an AE and should be reported as such only if deemed by the Investigator to be beyond the expected progression for OA.

Pre-existing conditions will be recorded in the eCRF system on the Medical History page.

A treatment-emergent AE (TEAE) will be defined as an AE that begins or that worsens in severity after at least one dose of IMP has been administered.

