4.3 Demographic and Background Variables

The following demographic and anthropometric information will be recorded at screening:

- Date of informed consent
- Medical and surgical history (including previous and current medical conditions and medications)
- Age calculated as (date of informed consent – date of birth)/365.25
- Gender
- Ethnic origin
- Race
- Height (cm)
- Body weight (kg)
- Body mass index (BMI) (kg/m^2)

Adverse Events from MIV-711-201 will be recorded as Medical history in MIV-711-202.

Concomitant medication in MIV-711-201 will be recorded as prior medication in MIV-711-202.

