9.1 Adverse Events

All AEs reported will be coded and classified according to MedDRA version 18.1. A treatment-emergent AE (TEAE) will be defined as an AE that begins or that worsens in severity after IMP has been administered.

Non-treatment emergent adverse events (NTEAE): AEs that occurred before the administration of IMP and did not worsen in severity or relationship after exposure to IMP.

All AE data as captured on the CRF for MIV-711-202 study will be listed by patient. All AEs from MIV-711-201 study for those patients admitted into the MIV-711-202 study will also be listed. All serious AEs (SAEs) will be listed. A listing of all AEs leading to treatment discontinuation will be presented.

Unless specified otherwise, all adverse event summaries will include the TEAEs only and adverse event summary counts of AEs will be the number of patients reporting adverse events and not the number of events reported. The number and percentage of patients with adverse events will be tabulated by body system (SOC) and preferred term (PT) for each group (A, B) and study (MIV-711-201, MIV-711-202). A patient with multiple adverse events within a body system is only counted once towards the total of that body system. If the same AE (preferred term) is reported several times for the same patient, it will only appear once for that specified treatment in the summary tables.

For patients with multiple adverse events of the same preferred term and of different severities, the AE with the highest assessment of severity will be used in the summaries presented by severity.

A general summary of all treatment-emergent adverse events will show the number and percentage of patients, as well as the number of events, according to the following categories:

- All treatment emergent adverse events
- ‘Related’ treatment emergent adverse events
- Mild treatment emergent adverse events
- Moderate treatment emergent adverse events
- Severe treatment emergent adverse events
- Serious treatment emergent adverse events
- Treatment emergent adverse events leading to early termination
- Deaths

Other summary tables for adverse events will include:

PAREXEL International Statistical Analysis Plan

Medivir
Protocol: MIV-711-202

Final 1.0
16 January 2018

- Number and Percentage of Patients with Treatment Emergent Adverse Events by System Organ Class, and Preferred Term

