- Number and Percentage of Patients with Treatment Emergent Adverse Events ‘Related to IMP’ by System Organ Class, Preferred Term, and Severity.
- Number and Percentage of Patients with Serious Treatment Emergent Adverse Events by System Organ Class, and Preferred Term
- Number and Percentage of Patients with Treatment Emergent Adverse Events Leading to Discontinuation by System Organ Class, and Preferred Term
- Number and Percentage of Patients with Treatment Emergent Adverse Events by Preferred Term per Frequency of Occurrence

All AE summary tables will display the AEs that occurred in both MIV-711-201 and MIV-711-202 studies for patients that were dosed in MIV-711-202. For tabulations of AEs by study group, any AE that starts on or after administration of the first dose received in MIV-711-201 and before the first dose received in MIV-711-202, will be assigned to the the 201 study group. Any AE occurring after the first dose administered in MIV-711-202 will be assigned to the 202 study group.

If a subject has multiple AEs with the same preferred term but occurring after each dose administration (MIV-711-201 and MIV-711-202), then one AE will be counted for each treatment administration. Adverse events that emerge in the first treatment period (201) and carry over into the next period (202) will be attributed to only the period in which the AE emerged (201). Such AEs that carry over into MIV-711-202 will be recorded as part of MIV-711-202 medical history.

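### The SAP's carry-over rule makes no exception for AEs that worsen, contrary to its own TEAE definition, so Group B worsening on first MIV-711 exposure can be missing from the 202 counts

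*SAP*

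**What the plan says.** **Definitions.** SAP 9.1 states: "A treatment-emergent AE (TEAE) will be defined as an AE that begins or that worsens in severity after IMP has been administered". Protocol 7.13.1 agrees: a TEAE "will be defined as an AE that begins or that worsens in severity after at least one dose of IMP has been administered". The SAP's complementary class, the non-treatment-emergent AE, is limited to "AEs that occurred before the administration of IMP and did not worsen in severity or relationship after exposure to IMP". SAP section 6 defines IMP by pointing to section 3.5, which describes only 200 mg MIV-711 once daily.

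**Tabulation.** Later in SAP 9.1, events are placed in a period by start date. The 201 period receives "any AE that starts on or after administration of the first dose received in MIV-711-201 and before the first dose received in MIV-711-202". For the extension, "Any AE occurring after the first dose administered in MIV-711-202 will be assigned to the 202 study group". A further sentence covers events that span the two studies: those that emerge in 201 and continue into 202 "will be attributed to only the period in which the AE emerged (201". They then enter 202 as medical history, as SAP 4.3 also says: "Adverse Events from MIV-711-201 will be recorded as Medical history in MIV-711-202".

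**Display.** The AE tables (14.3.1.1 to 14.3.1.6) show TEAEs in separate 201 and 202 columns for each group. According to SAP 2.3, Group B patients received placebo in 201.

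**The concern.** The definition and the tabulation rule can give different answers for the same event. By definition, an event that gets worse after the first MIV-711 dose is treatment-emergent on MIV-711. The carry-over sentence, applied as written, keeps it in 201 only.

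For Group B, the 201/202 boundary is also the boundary between placebo and active drug, so the choice of column decides which treatment the event is reported under. Safety over 26 weeks on 200 mg is the secondary objective for this group (SAP 2.3), and its analysis is descriptive. The counts in the 202 column are therefore the result itself. For events that carry over, the rule can lower those counts but cannot raise them.

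**Working it through.** The plan states no figure to reproduce here. The check applies both rules to the same cases.

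| Case | Carry-over and start-date rules | TEAE definition | Agree? |
|---|---|---|---|
| Starts in 201, ongoing, worsens after first 202 dose | 201 only | Emergent in 202 as well | No |
| Starts in 201, ongoing, does not worsen | 201 | 201 | Yes |
| Starts after first 202 dose | 202 | 202 | Yes |

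The conflict is confined to the first row.

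**Does the meaning of IMP rescue the rule?** Sections 6 and 3.5 make IMP 200 mg MIV-711, so a Group B event that began on placebo predates IMP. It would stay non-treatment-emergent only if it did not worsen. The tables nevertheless have a 201 TEAE column for Group B. If IMP is read loosely there to include blinded 201 medication, the event is already a TEAE in 201, but its worsening is still absent from 202. The consequence is the same on either reading.

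**Discontinuations.** Protocol 5.1 requires completion of 201 Visit 8 before roll-over. Read literally, a carried-over event that worsened and led to withdrawal from 202 would appear in Table 14.3.1.5 under 201, a study whose last treatment visit the patient had completed. Disposition Table 14.1.1 would show an AE withdrawal with no matching 202 TEAE.

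**Do other outputs show the worsening?** Table 14.1.7 counts AEs ongoing at rollover by system organ class and preferred term, without severity or change. The medical history listing (16.2.4.2) has no severity column. AEs from both studies are listed by patient, which helps a case-by-case reader but does not correct the tables.

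**Size, as illustration only.** Group B's size n is not stated; the SAP gives 50-80 patients for both groups together. Take n = 10, 20 or 30 as assumptions, and suppose one such patient is missing from a preferred term that has no other 202 cases. Incidence moves from 0/n to 1/n, shown with exact (Clopper-Pearson) 95% intervals.

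| n | Without the patient | With the patient | Change (1/n) |
|---|---|---|---|
| 10 | 0% (0 to 30.8) | 10.0% (0.3 to 44.5) | 10.0 points |
| 20 | 0% (0 to 16.8) | 5.0% (0.1 to 24.9) | 5.0 points |
| 30 | 0% (0 to 11.6) | 3.3% (0.1 to 17.2) | 3.3 points |

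These figures show the effect of one patient. They do not estimate how many patients are affected.

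**The case against.** The strongest reply is that the documents already provide a route. A 201 event ongoing at rollover becomes 202 medical history. Protocol 7.13.1 makes a pre-existing illness an AE if it worsens during treatment. A site following that rule would open a new 202 record, and SAP 9.1 would assign it to 202 by its start date. The SAP also counts a preferred term once for each treatment administration when it occurs after both. On this reading the carry-over sentence covers only the original, persisting record and prevents double counting.

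This is a fair reading, and it makes the harm conditional. It does not remove it, because the SAP never states the route and the word *only* can be taken to override it. Two programmers could produce different tables from the same text.

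Other points on this side also stand:

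- A reader might infer that the worsened event will be shown under placebo at its worsened grade. That would require someone to update the 201 AE record, and the 201 recording rules are not in these documents. The supportable statement is that the worsening can be missing from the 202 column.
- A reader might infer that the primary 52-week safety result is understated. In Group A both periods are on 200 mg, so the event stays under active drug and only changes column.
- A reader might try to size Group B from the placebo arm of 201 (240 / 3 = 80). The documents give no qualifying rate, and only patients at participating sites can enter.
- The affected set is narrowed further. Investigators can exclude patients for 201 findings (exclusion criterion 7), and expected progression of OA is not an AE (protocol 7.13.1).

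**Conclusion.** The conflict is real but narrow. SAP 9.1 attributes carried-over events to 201 alone, without the worsening exception that its own definitions and protocol 7.13.1 require. In Group B, an event that began on placebo and worsened after the first MIV-711 dose can be left out of the 202 TEAE counts. This depends on the site not having entered the worsening as a new 202 AE, or on the carry-over sentence being applied over that entry.

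The number of such events cannot be estimated from the documents. Each affected patient moves a term's incidence by 1/n, and the values of n used above are assumptions. Sample size and power are untouched, since the study is not powered for any confirmatory analysis (protocol 9.2.1). The wording should be corrected, but the point does not undermine the safety evaluation as a whole.

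**What to change.** Replace the carry-over sentence in SAP 9.1 with wording such as:

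> *An AE that emerged in 201 and continues into 202 without worsening is attributed to 201 only. If it worsens in severity or relationship after the first 202 dose, the worsening is counted as a 202 TEAE at the worsened grade, using the 202 AE record, whose start date is the date of worsening. The original record remains in 201 at its pre-202 grade.*

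Three details matter.

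- **Relationship.** The non-TEAE definition excludes worsening in relationship, while the TEAE definition names severity only. Including relationship in the new sentence, and aligning the TEAE definition with it, closes that gap.
- **Seriousness.** It may be tempting to add becoming serious as a trigger. That is not part of the TEAE definition and is not needed here.
- **Date of worsening.** The AE fields in protocol 7.13.2.5 include onset, resolution and intensity, but no date for a change of grade. The rule therefore has to rest on a separate 202 AE record, as protocol 7.13.1 implies. Sites should be told to enter one.

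The cost is slightly higher 202 AE counts, plus a check before database lock of 201 AEs ongoing at rollover against 202 AE records, with queries where worsening was noted but no 202 record exists.

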9.2 Clinical Safety Laboratory Tests (Hematology, Chemistry, Urinalysis)

9.2.1 Hematology and Chemistry

A by-patient listing of all observed chemistry and hematology laboratory data will be provided. Laboratory results outside the normal range will be flagged. The abnormal values will be flagged with ‘L’ (low) for values below the lower limit of the laboratory’s normal range or ‘H’ (high) for values above the upper limit of the laboratory’s normal range. Abnormal values will be graded as not clinically significant (NCS) or clinically significant (CS). Clinically significant laboratory results will be included in the AE listings.

The observed values of all safety laboratory assessments for clinical chemistry and hematology will be summarized using descriptive statistics showing the number of

PAREXEL International Statistical Analysis Plan

Medivir
Protocol: MIV-711-202

Final 1.0
16 January 2018

observations (n), mean, median, SD, minimum, and maximum value. Table summaries will be presented by time point.

Baseline values for all clinical chemistry and hematology parameters will be categorized as being below the normal range (Low), within the normal range (Normal), and above the normal range (High). In addition, the minimum and maximum score over visits post baseline will be calculated and categorized into Low, Normal and High. Note that the minimum/maximum are taken over visits post the baseline visit, i.e. visits when the patients are on 200 mg MIV-711. Shift from baseline tables of the minimum category score and the maximum category score will be tabulated displaying frequency counts and percentage of patients in each (low, normal, high)-matrix by study group.

All hematology, chemistry, and coagulation, laboratory parameters noted in Section 4.4.2 of this SAP will be tabulated.

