- Serum transaminases (alanine aminotransferase [ALT] and/or aspartate aminotransferase [AST]) > 3 x upper limit of normal (ULN) AND total bilirubin > 2 x ULN (confirmed by subsequent repeat).
- ALT or AST > 3 x ULN (confirmed by repeat visit) with the appearance or worsening of symptoms felt by the Investigator to be potentially related to hepatic inflammation, such as fatigue, nausea, vomiting, right upper quadrant pain or tenderness, fever, rash, or eosinophilia.
- QTcF > 500 ms or increase > 60 ms from time matched baseline (confirmed by repeat

ECG).

- Occurrence of an exclusion criterion which is clinically relevant and affects the patient's safety, if discontinuation is considered necessary by the Principal Investigator and/or Sponsor.

In order to perform the modified intention to treat (mITT) analysis, and to enable safety analyses, all patients who discontinue their medication will be asked to still complete their follow-up visit (Visit 6) as outlined in the study schedule.

Patients who withdraw from the study will not be replaced.

In all cases, the reason(s) for withdrawal must be recorded on the electronic CRF (eCRF).

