## 7 ENDPOINT AND METHODS OF ASSESSMENT

### 7.1 Primary Endpoint (Study Population A)

The primary objective is to study the safety and tolerability of MIV-711 in OA patients who have received treatment for up to 52 (26+26) weeks.

Safety endpoints:

- Incidence and severity of AEs
- Incidence and severity of clinical laboratory abnormalities
- Physical examination findings by patient
- Incidence and severity of ECG abnormalities
- Mean change from Baseline (Visit 2 of Study MIV-711-201) in vital signs (blood pressure, heart rate, temperature) and oxygen saturation
- Categorical summary of observed vital signs and vital sign changes compared to Baseline (Visit 2 of Study MIV-711-201), by patient

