### **9.5.4 Safety**

The primary purpose and endpoint of the present study is safety and tolerability as described above. There will be no formal statistical hypothesis testing for safety data in this study, therefore only summary statistics will be provided. Safety summaries will be presented by scheduled assessment for the SAF. Summary statistics (number of observations, mean, SD, median, minimum and maximum values) will be presented for continuous variables, and number and percentages (n, %) will be presented for categorical variables. Where applicable, changes from Baseline will also be summarised over time.

Treatment-emergent adverse events will be summarised by preferred term and system organ class and classified according to the latest version of coded Medical Dictionary for Regulatory Activities (MedDRA). The number and percentage of TEAEs will be summarised by system organ class and preferred term in the SAF. Treatment-emergent adverse events will be further summarised with respect to severity and relationship to IMP. Treatment-emergent adverse events related to IMP, leading to withdrawal, serious TEAEs, and deaths will be summarised.

Clinical laboratory tests (haematology, serum chemistry), ECG, and vital signs will be summarised for the SAF at each scheduled assessment. Potentially clinically important findings will also be summarised and listed.

The number of patients taking rescue medication (see definition in Section 6.6.1), the amount of rescue medication taken and the reason for use will be tabulated and summarised descriptively.

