Table 14.3.1.6	Number and Percentage of Patients with Treatment Emergent Adverse Events by Frequency, Preferred Term, and Group
Table 14.3.2.1	Clinical Laboratory Chemistry Summary of Observed Values, SAF Population
Table 14.3.2.2	Clinical Laboratory Hematology Summary of Observed Values, SAF Population
Table 14.3.2.3	Clinical Laboratory Chemistry – Shift From Baseline to Maximum Value, SAF Population
Table 14.3.2.4	Clinical Laboratory Chemistry – Shift From Baseline to Minimum Value, SAF Population
Table 14.3.2.5	Clinical Laboratory Hematology – Shift From Baseline to Maximum Value, SAF Population
Table 14.3.2.6	Clinical Laboratory Hematology – Shift From Baseline to Minimum Value, SAF Population
Table 14.3.3	Vital Signs Blood Pressure and Heart Rate Summary of Observed and Change from Baseline Values, SAF Population
Table 14.3.4.1	12 Lead ECG – Summary of Observed and Change from Baseline Values SAF Population
Table 14.3.4.2	12-Lead ECG – Categorical Summary of Observed Values, SAF Population
Table 14.3.4.3	12-Lead ECG – Categorical Summary of Change From Baseline, SAF Population

PAREXEL International Statistical Analysis Plan

Medivir
Protocol: MIV-711-202

Final 1.0
16 January 2018

12. Figures

TLF Number	Title
Figure 14.2.1.1	Estimated Mean \pm 95% CI for MRI of Bone Area by Week and Group, ITT Population
Figure 14.2.1.2	Estimated Mean \pm 95% CI for MRI of Cartilage Thickness by Week and Group, ITT Population
Figure 14.2.1.3	Estimated Mean \pm 95% CI for MRI of Total BML Volume by Week and Group, ITT Population
Figure 14.2.1.4	Estimated change from Visit 2 MIV-711-201 \pm 95% for MRI of Bone Area by Week and Group, ITT Population
Figure 14.2.1.5	Estimated change from Visit 2 MIV-711-201 \pm 95% for Cartilage Thickness by by Week and Group, ITT Population
Figure 14.2.1.6	Estimated change from Visit 2 MIV-711-201 \pm 95% for MRI of Total BML Volume by Week and Group, ITT Population
Figure 14.2.1.7	Estimated change from Visit 2 MIV-711-201 \pm 95% for MRI of Bone Area by Week and Group, PPS Population
Figure 14.2.1.8	Estimated change from Visit 2 MIV-711-201 \pm 95% for Cartilage Thickness by Week and Group, PPS Population
Figure 14.2.1.9	Estimated change from Visit 2 MIV-711-201 \pm 95% for MRI of Total BML Volume by Week and Group, PPS Population
Figure 14.2.3.1	Estimated Mean \pm 95% CI for NRS Items by Week and Group, ITT Population

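### No laboratory table counts patients by severity, clinical significance or threshold exceedance, although severity is part of the primary endpoint

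*SAP*

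**What the plan says.** Protocol 7.1, repeated in 9.5.1, lists "Incidence and severity of clinical laboratory abnormalities" among the primary safety endpoints for Study Population A. Protocol 7.3 makes the same endpoints secondary for Study Population B. Protocol 9.5.4, directly after naming laboratory tests, ECG and vital signs, adds: "Potentially clinically important findings will also be summarised and listed".

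SAP 9.2.1 handles chemistry and hematology in three ways.

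- Descriptive tables: "The observed values of all safety laboratory assessments for clinical chemistry and hematology will be summarized using descriptive statistics", by time point. In SAP section 11 these are Table 14.3.2.1, "Clinical Laboratory Chemistry Summary of Observed Values, SAF Population", and its hematology counterpart 14.3.2.2.
- Shift tables: the baseline value and the post-baseline minimum and maximum are "categorized as being below the normal range (Low), within the normal range (Normal), and above the normal range (High". These are Tables 14.3.2.3 to 14.3.2.6, for example "Clinical Laboratory Chemistry – Shift From Baseline to Maximum Value, SAF Population".
- Clinical rating: "Abnormal values will be graded as not clinically significant (NCS) or clinically significant (CS". The rating appears in the laboratory listings (16.2.8.1 to 16.2.8.4), and significant results also go to the adverse event listings.

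Under SAP 9.2.2, urinalysis is listed and not tabulated.

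**The concern.** The endpoint has two parts. The shift tables largely serve incidence for chemistry and hematology, because they count patients who move out of range. Severity has no laboratory table. The SAP defines no grade, no ULN-multiple category and no criterion for a clinically important laboratory value, and the CS/NCS rating that is collected is not counted anywhere.

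At stake is whether the clinical study report can answer a question that the protocol itself poses. If the SAP is followed as written, no table states how many patients in each group had a severe or clinically significant laboratory abnormality. A reader would have to count by hand from the listings, using criteria chosen after seeing the data. SAP 4.6 openly records a departure from the protocol over analysis populations. It records none here, so this looks like an oversight and not a decision.

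**Working it through.** The plan states no figure to reproduce, and no power or sample size calculation depends on this point. The check sets what the protocol asks for against what the SAP's outputs can deliver.

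**Step 1: count the tables.** SAP section 11 lists laboratory Tables 14.3.2.1 to 14.3.2.6.

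- Descriptive, by visit: 2
- Low/Normal/High shift: 4
- By severity, CS/NCS status or threshold: 0
- Total: 2 + 4 + 0 = 6

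**Step 2: what a shift table can separate.** A value is High when it exceeds 1 x ULN. For illustration, a transaminase at 1.1 x ULN and one at 10 x ULN both fall in the High row. The table gives the number of patients above range and says nothing about how far above.

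**Step 3: what a descriptive table can separate.** Each visit shows the group minimum and maximum, so one very high value would be visible. The number of patients above a threshold cannot be recovered. A maximum above 3 x ULN at several visits fits one patient throughout or a different patient each time. Parameters are summarised separately, so a raised ALT maximum and a raised bilirubin maximum cannot be placed in the same patient.

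**Step 4: the adverse event route.** Under Protocol 10.6, a laboratory change that the investigator judges clinically significant is an adverse event. It can then enter the SAP 9.1 tables, but three features limit this.

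- Protocol 7.13.2.2 defines intensity by interference with usual activities. A large rise without symptoms can properly be rated mild.
- Table 14.3.1.1 pools mild, moderate and severe events of all kinds. Severity by preferred term is tabulated only for related events (Table 14.3.1.3).
- Protocol 7.13.2.4 provides for no adverse events of special interest, so no separate laboratory event table arises that way.

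**Step 5: compare with ECG.** Protocol 5.3 lists withdrawal criteria that include "Serum transaminases (alanine aminotransferase [ALT] and/or aspartate aminotransferase [AST") above 3 x ULN with total bilirubin above 2 x ULN, ALT or AST above 3 x ULN with symptoms, and QTcF above 500 ms or an increase above 60 ms. SAP 9.4 counts patients above 500 msec and with changes above 60 msec, by time point and group. The liver multiples in the same protocol list have no table.

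**Step 6: repeat tests.** SAP section 6, in line with Protocol 9.2.2, uses the original assessment for post-dose summaries. A peak seen only on a repeat or unscheduled test therefore appears in listings and not in the planned tables. The Protocol 5.3 liver criteria call for confirmation by repeat, so any count has to say which tests it uses.

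**The case against.** The strongest reply is that the information is present. Tables 14.3.2.1 and 14.3.2.2 show extremes at each visit. Listing 16.2.8.1 gives every patient's value with its flag and CS/NCS rating. Clinically significant changes reach the adverse event tables, where the protocol's only severity scale applies. The study is small, descriptive and not powered for confirmatory analysis (Protocol 9.2.1), so a reader could count from the listings.

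Much of this stands, and it rules out several stronger readings that a reader might infer.

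- That laboratory results are tabulated solely as low, normal or high. The descriptive tables contradict this.
- That severity goes entirely unreported, or that an extreme value cannot be told from a trivial one. That is true within a shift table, but not across visit maxima, listings and adverse event tables together.
- That one affected patient can be expressed as a share of the 50 to 80 expected. That range covers Populations A and B combined, and Protocol 5.4 says the total may fall outside it. The primary endpoint concerns Population A, whose size is not stated.
- That the Protocol 5.3 multiples are severity grades or stand-alone limits. They are parts of withdrawal criteria that require confirmation, and require either both abnormalities or accompanying symptoms.
- That the withdrawal from MIV-711-201 for raised liver tests shows a drug signal. Protocol 2.2 reports it from blinded data, and a patient withdrawn before Visit 8 could not meet Inclusion Criterion 1 here.

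A fair criticism of the remedy is that outside the liver tests it separates only significant from not significant, and that this rating rests on investigator judgement. It is a limited answer on severity. It still supplies a count, and Protocol 9.5.4 promised a summary in addition to a listing.

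**Conclusion.** The point holds as a reporting gap. Of six planned laboratory tables, none counts patients by severity, CS/NCS status or threshold exceedance. Severity is a named part of the primary endpoint, and the protocol promises a summary of findings that may be clinically important. The other outputs can reveal individual extreme values, but they give no patient count, and adverse event intensity is not a grade of the laboratory value.

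The gap concerns laboratory data; QT and QTc already have threshold tables. It biases no estimate and affects no test, since none is planned for safety. No percentage can be attached to it without the size of each group. The conclusion assumes that the SAP's table list and shells are the complete set of planned summaries. The change should be made.

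**What to change.** Add one table to SAP 9.2.1 and section 11, by group, on the safety population, giving:

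- (a) for each laboratory parameter, the number and percentage of patients with any post-baseline value that the investigator rated clinically significant;
- (b) the number and percentage of patients whose worst post-baseline ALT or AST exceeds 3 x ULN, whose bilirubin exceeds 2 x ULN, and who have both.

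Use the same post-baseline visits as the shift tables, and say whether the two exceedances in the last category of (b) must fall at the same visit. Label (b) as reporting categories that borrow the multiples from the Protocol 5.3 withdrawal criteria. They are not severity grades and set no clinical rule. State whether repeat and unscheduled tests count, because SAP section 6 would otherwise restrict post-dose summaries to the original assessment.

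The cost is one extra summary table. Values, normal ranges and CS/NCS ratings are already collected, and nothing changes in study conduct.
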